7.2.3 Secondary endpoint analyses

[figure not shown]
For the list of key secondary and secondary endpoints, refer to [Section 2.1.3](#). Summary statistics will be presented for each endpoint, and at each visit if appropriate.

The key secondary endpoints are both binary in nature and will be analysed using frequency tables, risk differences, 95% confidence intervals and p-values. The delta method and average marginal effect (AME) method will be used. In the NIV cohort, adjustment will be made for the number of days under NIV support, baseline D-Dimer level and age. For the IMV cohort, adjustment will be made for the baseline WHO value, baseline D-Dimer level and age.

For the safety endpoint (MBE to Day 6) which is binary, the Chang and Zhang exact method will be used, without adjustment for covariates.

The continuous endpoints will be analysed descriptively and inferentially, albeit in a non- confirmatory manner. A restricted maximum likelihood (REML) based ANCOVA will be used. In the NIV cohort, adjustment will be made for the number of days under NIV support, baseline D-Dimer level and age. For the IMV cohort, adjustment will be made for the baseline WHO value, baseline D-Dimer level and age. The treatment difference with 95% confidence interval will be presented.

More detailed descriptions will be provided in the TSAP.

7.2.5 Safety analyses

Adverse events will be coded using the Medical Dictionary for Drug Regulatory Activities (MedDRA). Standard BI summary tables and listings will be produced. All adverse events with an onset between start of treatment and end of the REP, as defined in [Section 1.2.](#), will be assigned to the on-treatment period for evaluation.

All treated patients will be included in the safety analysis. In general, safety analyses will be descriptive in nature and will be based on BI standards. No hypothesis testing is planned.

Statistical analysis and reporting of adverse events will concentrate on treatment-emergent adverse events, i.e. all adverse events occurring between start of treatment and end of the REP. Adverse events that start before first drug administration and deteriorate under treatment will also be considered as 'treatment-emergent'.

Frequency, severity, and causal relationship of adverse events will be tabulated by system organ class and preferred term after coding according to the current version of MedDRA at DBL.

Laboratory data will be analysed quantitatively and qualitatively. The latter will be done via comparison of laboratory data to their reference ranges. Values outside the reference range as well as values defined as clinically relevant will be summarised. Treatment arms will be compared descriptively with regard to distribution parameters as well as with regard to frequency and percentage of patients with abnormal values or clinically relevant abnormal values.

Vital signs, physical examinations, or other safety-relevant data observed at screening, baseline, during the course of the trial and at the end-of-trial evaluation will be assessed with regard to possible changes compared with findings before start of treatment.

Further details on the safety analysis will be specified in the TSAP.

7.2.6 Interim Analyses

One interim analysis is planned after the first (approximately) 60 patients (Part 1). An independent DMC will review the efficacy and safety data and provide a recommendation regarding the continuation of the trial into Part 2 and the corresponding dose for the alteplase treatment arm. The DMC charter will lay out the general principles of decision-making of the DMC. Further details on the DMC are described in [Section 8.7](#).

7.3 HANDLING OF MISSING DATA

For the analysis of the primary endpoint, time to clinical improvement or hospital discharge up to Day 28, patients will be censored at Day 28 if they die prior to Day 28, at the time they received bail-out therapy, or have not had clinical improvement by Day 28.

With respect to safety evaluations, it is not planned to impute missing values.

7.4 RANDOMISATION

BI will arrange for the randomisation and the packaging and labelling of trial medication. The randomisation list will be generated using a validated system, which involves a pseudo-random number generator so that the resulting treatment will be reproducible and non-predictable. The block size will be documented in the CTR. Access to the codes will be controlled and documented.

Randomisation in Part 1 will be to the three treatment arms of:

- alteplase 0.3mg/kg over 2 hours followed by 0.02 mg/kg/h over 12 hours “dosing regimen A”
- alteplase 0.6 mg/kg over 2 hours followed by 0.04 mg/kg/h over12 hours “dosing regimen B”
- SOC

With an allocation ratio of 1:1:1, with stratification by the following factor:

- Type of ventilation (non-invasive or invasive mechanical)

Randomisation in Part 2 will be to alteplase and to standard of care, with an allocation ratio of 2:1, with stratification by the following factors:

- Type of ventilation (non-invasive or invasive mechanical)
- D-Dimer levels (\geq ULN to <5 -fold ULN, versus ≥ 5 -fold ULN)

7.5 DETERMINATION OF SAMPLE SIZE

Part 1 of the study plans to randomise approximately 60 patients in total, with a view to exploring the data in a descriptive manner.

Sample size considerations are limited to Part 2 and the NIV patient cohort.

Part 2 has a planned confirmatory analysis at the 2-sided type I error level of alpha=5% with a power of 85% to 90%, applicable to the first two steps within the pre-planned hierachial testing procedure. The trial uses a randomisation allocation ratio of 2:1, which leads to approximately 140 NIV patients on the treatment arm and approximately 70 NIV patients on the SOC alone.

With regard to the primary analysis of the primary endpoint, H0_1 in the hierarchy testing procedure, in the NIV patient cohort, a hazard ratio of 2.0 is assumed, with event rates in the SOC alone group and alteplase group of approximately 30% and 50%. In the alteplase arm, it is expected to have a median time to event of 20 to 30 days.

With regard to the primary analysis of the key secondary endpoint “Treatment failure at Day 28”, H0_2 in the hierarchy testing procedure, in the NIV patient cohort, a risk difference of -20% is assumed, with event rates in the SOC alone group and alteplase group of approximately 40% and 20%.

With regard to the primary analysis of the key secondary endpoint “All cause mortality at Day 28”, H0_3 in the hierarchy testing procedure, in the NIV patient cohort, there would be a power of 85% under the assumptions of a risk difference of -16%. This would be with event rates in the SOC alone group and alteplase group of approximately 25% and 9%. These are very similar event rates as observed in Part 1.

The sample size determination or justification is in line with the null hypotheses and hierachial testing approach as defined in [Section 7.1](#), whereby it is planned to test for superiority of alteplase vs SOC alone in the NIV patient cohort. Whilst the assumptions are still rather approximate, the magnitude of these assumptions is similar to the available results

in other COVID-19 patients [[R20-2001](#), [R20-2246](#)] and to the results observed in Part 1 of this study. In this emerging disease and during this pandemic, standard of care is evolving, and other factors are having an influence, for example, the introduction of vaccines.

Calculations were performed using the software R Version 3.6.1 and nQuery Version 4.0.

Only patients randomised into Part 1 will be included in the analyses of Part 1, and only patients randomised into Part 2 will be included in the confirmatory analyses of Part 2.

8. INFORMED CONSENT, TRIAL RECORDS, DATA PROTECTION, PUBLICATION POLICY, AND ADMINISTRATIVE STRUCTURE

The trial will be carried out in compliance with the protocol, the ethical principles laid down in the Declaration of Helsinki, in accordance with the ICH Harmonized Guideline for GCP, relevant BI SOPs, the EU directive 2001/20/EC / EU regulation 536/2014 and other relevant regulations. Investigators and site staff must adhere to these principles. Deviation from the protocol, the principles of ICH-GCP or applicable regulations as will be treated as “protocol deviation”.

Standard medical care (prophylactic, diagnostic and therapeutic procedures) remains the responsibility of the treating physician of the patient.

The investigator should inform the sponsor immediately of any urgent safety measures taken to protect the trial patients against any immediate hazard, as well as of any serious breaches of the protocol or of ICH-GCP.

The BI transparency and publication policy can be found on the following web page: <https://trials.boehringer-ingelheim.com/>. The rights of the investigator and of the sponsor with regard to publication of the results of this trial are described in the investigator contract. As a rule, no trial results should be published prior to finalisation of the CTR.

The certificate of insurance cover is made available to the investigator and the patients and is stored in the ISF.

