A case series of five patients with COVID-19-associated ARDS receiving a bolus administration of alteplase (50 mg) and three patients with an additional re-bolus and concomitant heparin treatment and alteplase appeared to have an improved respiratory status following alteplase [[P20-04591](#)]. In a study with three severe COVID-19 related ARDS patient under mechanical ventilation, the administration of an intravenous bolus of alteplase (25 mg) followed by an infusion of 25 mg over 22 hours, led to a temporary improvement in their respiratory status (ranging from 38% to a ~100% improvement), with one of them having a sustained response, the two others having transient improvements [[P20-03126](#)]. A further study with four severe COVID-19 related patients with ARDS, under mechanical ventilation and a bolus-infusion concept (50 mg over 2 hours) showed a post treatment immediate improvement in gas exchange and/or hemodynamics [[P20-04704](#)]. The authors concluded that thrombolysis improved alveolar ventilation by restoring blood flow to previously occluded regions.

Results of phase II (Part 1)

Efficacy

Observed data from Phase II (Part 1), in line with the dose-finding objective, demonstrated the alteplase 0.6/0.04 mg/kg dose in addition to SOC was associated with faster clinical improvement or hospital discharge, compared with the alteplase 0.3/0.02 mg/kg + SOC, or SOC alone treatments.

Data from patients in the alteplase 0.6/0.04 mg/kg group show numerically more favourable outcomes of clinical improvement of ≥ 2 points on the 11-point WHO Clinical Progression

Scale or hospital discharge by Day 28 than those in the SOC group (adjusted HR 2.04 [95% CI 0.83 to 5.01], $p=0.1183$). The alteplase 0.6/0.04 mg/kg group had a median time of 19 days to clinical improvement or hospital discharge; the median was not achieved in the alteplase 0.3/0.02 mg/kg or the SOC groups. No difference on the primary endpoint was observed between the alteplase 0.3/0.02 mg/kg and the SOC groups.

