The favorable results on the primary endpoint in the alteplase 0.6/0.04 mg/kg dosing group were supported by similar trends for other prespecified analyses, including sensitivity analyses of the primary endpoint, as well as secondary efficacy endpoints of lower all-cause mortality and lower all-cause mortality or mechanical ventilation up to Day 28 compared with the SOC group, greater improvement in median $\text{PaO}_2/\text{FiO}_2$ ratio from baseline to Day 6 and more ventilator-free days from the start of treatment to Day 28 than in the alteplase 0.3/0.02 mg/kg and SOC groups.

A Kaplan-Meier estimate of the unadjusted primary analysis showed a separation of the alteplase 0.6/0.04 mg/kg group compared with the other two treatment groups, beginning at approximately Day 11. The risk difference for the alteplase 0.6/0.04 mg/kg group compared with the SOC group at Day 28 was 19.1% in favour of alteplase (95% CI -10.6%, 48.8%).

[REDACTED]

Secondary and further endpoint results supported the clinical benefit of alteplase in addition to SOC, particularly for the alteplase 0.6/0.04 mg/kg group. Both alteplase groups had numerically fewer cases of all-cause mortality than in the SOC group at Day 28. All-cause mortality or mechanical ventilation at Day 28 was considered as treatment failure; both alteplase groups had fewer cases of all-cause mortality or mechanical ventilation at Day 28 than the SOC group. The alteplase 0.6/0.04 mg/kg group had more ventilator-free days from the start of treatment to Day 28 than the alteplase 0.3/0.02 mg/kg and SOC groups. In addition, the alteplase 0.6/0.04 mg/kg group had a greater improvement in median $\text{PaO}_2/\text{FiO}_2$ ratio from baseline to Day 6 compared with the alteplase 0.3/0.02 mg/kg or SOC group..

[REDACTED]

Safety

The overall safety results were generally comparable across the treatment groups. Patients treated with alteplase and those receiving only standard of care had similar frequencies of any adverse events (AEs), severe AEs, and serious AEs. The majority of reported AEs were of mild or moderate intensity. No new safety signals were identified.

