The null hypothesis to be tested for the key secondary endpoint 'Treatment failure at Day 28' in the NIV patient cohort is that the risk difference between alteplase and SOC alone equals 0. The alternative hypothesis is that the risk difference between alteplase and SOC alone is not equal to 0. Superiority will be declared if the risk difference between alteplase and SOC alone is significantly less than 0 at the two-sided type I error level alpha=5%.

H0_3:

The null hypothesis to be tested for the key secondary endpoint 'All cause mortality at Day 28' in the NIV patient cohort is that the risk difference between alteplase and SOC alone equals 0. The alternative hypothesis is that the risk difference between alteplase and SOC alone is not equal to 0. Superiority will be declared if the risk difference between alteplase and SOC alone is significantly less than 0 at the two-sided type I error level alpha=5%.

In the first step, the primary endpoint hypothesis (H0_1) will be tested at the 2-sided type I error level of alpha=5%. If the null hypothesis (H0_1) is rejected, the key secondary endpoint hypothesis (H0_2) based on the endpoint Treatment failure at Day 28 will then be tested in a second step, again at alpha=5%. If the null hypothesis (H0_2) is rejected, the remaining key secondary endpoint hypothesis (H0_3) based on the endpoint all cause mortality at Day 28 will then be tested in a third step, again at alpha=5%.

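### Protocol 7.5 overstates power at its own inputs, before covariate adjustment: H0_1 is about 82–83% (stated 85–90%) and H0_3 about 82% (stated 85%)

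*Protocol*

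**What the plan says.** Protocol 7.5 sizes Part 2 on the NIV cohort only, with 2:1 allocation (about 140 alteplase, 70 SOC) at two-sided 5%, "with a power of 85% to 90%, applicable to the first two steps within the pre-planned hierachial testing procedure".

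- **H0_1 (time to improvement or discharge):** "a hazard ratio of 2.0 is assumed, with event rates in the SOC alone group and alteplase group of approximately 30% and 50" per cent. The section adds: "In the alteplase arm, it is expected to have a median time to event of 20 to 30 days".
- **H0_2 (treatment failure at Day 28):** about 40% SOC against 20% alteplase.
- **H0_3 (mortality at Day 28):** "there would be a power of 85% under the assumptions of a risk difference of -16" percentage points, from about 25% SOC to 9% alteplase.

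On method it says only: "Calculations were performed using the software R Version 3.6.1 and nQuery Version 4.0". No formula is named and no gain from covariates is claimed.

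The planned tests are a covariate-adjusted Cox model with a Wald p-value (Protocol 7.2.2; Part 2 SAP 7.4.1) and, for the two key secondary endpoints, logistic regression with average marginal effects and delta-method intervals (Protocol 7.2.3; Part 2 SAP 7.5.1.1).

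**The concern.** The three stated powers are what common closed-form approximations give, but those approximations do not match the planned tests well in this setting. With 2:1 allocation to the arm expected to have more primary events, SOC contributes few events, and Schoenfeld's formula is then too favourable. For mortality, the more variable arm (SOC) is also the smaller one, so a pooled-variance formula gives more power than a Wald-type risk difference.

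Section 7.5 is the only justification given for 210 NIV patients. Testing is also strictly sequential: "If the null hypothesis (H0_1) is rejected, the key secondary endpoint hypothesis (H0_2) based on the endpoint Treatment failure at Day 28" is tested next, so a miss on H0_1 ends the confirmatory procedure. A reader told 85–90% expects a 10–15% chance of missing H0_1 under the assumed effect. Before adjustment the chance is about 17–18%.

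**Working it through.** **Inputs.** From Protocol 7.5: 70 SOC and 140 alteplase patients; two-sided alpha 0.05; HR 2.0 with about 30%/50% events; 40%/20%; 25%/9%. From Protocol 7.2.2: censoring at Day 28 and a Wald test. No dropout is stated, so none is used.

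**1. Reproducing the stated figures.**

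- H0_1, Schoenfeld: events = 0.30×70 + 0.50×140 = 21 + 70 = 91. Power = Φ(√(91×2/9)×ln 2 − 1.96) = Φ(3.117 − 1.96) = 87.6%.
- H0_2, pooled variance under the null: pooled rate = 56/210 = 0.267; SE₀ = √(0.267×0.733×(1/70+1/140)) = 0.0647; SE₁ = √(0.24/70+0.16/140) = 0.0676. Power = Φ((0.20 − 1.96×0.0647)/0.0676) = 86.0%.
- H0_3, same formula: pooled rate = 30.1/210 = 0.143; SE₀ = 0.0513; SE₁ = √(0.1875/70+0.0819/140) = 0.0571. Power = Φ((0.16 − 1.96×0.0513)/0.0571) = 85.1%.

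All three agree with Section 7.5.

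**2. Do the H0_1 inputs agree?** Under proportional hazards, HR 2.0 with 30% SOC gives 1 − 0.70² = 51% alteplase. HR 2.0 with 50% alteplase gives 1 − √0.50 = 29.3% SOC. A 50% rate at Day 28 puts the alteplase median at 28 days, inside 20–30. The set is coherent within rounding.

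**3. H0_1 under a Cox Wald test.** Schoenfeld's factor 2/9 treats a third of the 91 events (about 30) as SOC events; the stated rates give 21. Simulated power of an unadjusted Cox Wald test (exponential times, censored at Day 28, 20,000 runs per setting) at HR 2.0:

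| SOC / alteplase events | Alteplase median (days) | Power |
|---|---|---|
| 30% / 51% | about 27 | 83.2% |
| 29.3% / 50% | 28 | 82.0–82.2% (two runs) |
| 32.2% / 54.0% | 25 | 85.2% |
| 37.0% / 60.3% | 21 | 89.4% |
| 38.4% / 62.1% | 20 | 91.0% |
| 27.6% / 47.6% | 30 | 79.9% |

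The log-rank test gives 83.8% and 82.5% for the first two rows. Recording times by day, with Weibull shapes 0.5, 1 and 2, gives 81.5%, 82.3% and 82.1% at 30%/51%, so the result does not rest on exponential times. At HR 2.0, 85–90% needs medians of about 21–25 days, hence Day 28 differences of 21.8 (54.0 − 32.2) to 23.3 (60.3 − 37.0) points. Section 7.5 states 20.

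**4. H0_3 under a Wald-type risk difference.** The unadjusted counterpart of the delta-method test uses the unpooled variance: Φ(0.16/0.0571 − 1.96) = 80.0% by normal approximation, and 82.2% by exact enumeration of both binomials. The exact figure is the one to use.

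**5. H0_2 the same way.** Φ(0.20/0.0676 − 1.96) = 84.1%; exact 84.9%. This is in effect as stated.

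**6. What adjustment could add (assumption).** The documents give no prognostic strength. With one normal covariate, and marginal rates held at the stated values (3,000–4,000 runs):

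| Covariate effect (log scale, per SD) | H0_1 at 30/51 | H0_3 |
|---|---|---|
| 0 | 83.1% | 82.4% |
| 0.25 | 83.9% | 82.1% |
| 0.5 | 86.8% | 83.2% |
| 0.7 | 90.6% | 85.5% |

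Reaching 85% takes a strength between 0.25 and 0.5 per SD for H0_1 and about 0.7 (odds ratio about 2.0 per SD) for H0_3.

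**The case against.** The strongest reply is that nothing was miscalculated. Every stated power follows from a standard formula and the stated inputs, and Section 7.5 calls its assumptions approximate. The planned tests are adjusted, so unadjusted power is not the power of the trial. Protocol 1.1 links raised D-dimer to poorer outcome and older age to severe disease, and both are model covariates; a modest effect would close the H0_1 gap. This largely stands, and it keeps the point small. It does not remove it: Section 7.5 claims no covariate gain, and its caveat concerns the size of the assumed effects, not the power method.

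Four stronger readings are tempting, and the documents do not support them:

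- **The H0_1 inputs contradict one another.** Rates of exactly 30% and 50% imply HR ln 0.5/ln 0.7 = 1.94, with simulated power of 79–80%. But the rates are given as approximate, and HR 2.0 is the stated effect for an adjusted model. With a covariate of strength 0.40 per SD (an assumption), a conditional HR of 2.0 gives marginal rates of 30.0% and 50.0%. Setting 79–80% against 85–90% compares two effect sizes.
- **The median range is itself an error.** It is worded as an expectation, and 28 days lies inside it.
- **Part 1 rules out the rates that would support 85–90%.** In Part 1 the selected dose "group had a median time of 19 days to clinical improvement or hospital discharge", and the risk difference "at Day 28 was 19.1% in favour of alteplase" (95% CI −10.6% to 48.8%). That result is small and imprecise, it is not presented as an NIV result, and neighbouring text is redacted. It neither supports nor excludes 22–23 points in NIV patients.
- **The chance of passing all the steps is much lower than stated.** Section 7.5 gives power hypothesis by hypothesis and makes no cumulative claim, and the documents give no joint distribution from which to calculate one.

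**Conclusion.** The concern holds in a limited form. At HR 2.0 with rates that round to 30%/50%, H0_1 power is about 82–83%, which is 2–3 points below the lower end of the stated range. H0_3 power at 25%/9% is about 82%, 3 points below the stated 85%. H0_2, at about 85%, is sound.

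These figures assume 70 and 140 patients, no dropout, proportional hazards, censoring at Day 28 and no covariate adjustment. The cause is the optimism of standard approximations under this allocation, not a calculation error. Adjustment may recover the difference, but the documents do not allow that gain to be quantified.

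**What to change.** Change wording in Protocol 7.5 only:

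1. Restate H0_1 power as about 82–83% at HR 2.0 with about 30%/50% events and a median of about 28 days. Alternatively, keep 85–90% and state the rates that support it (about 54–60% against 32–37%, median about 21–25 days) and why they are expected in NIV patients.
2. Restate H0_3 power as about 82%. Leave H0_2 at about 85%.
3. Label the H0_1 and H0_3 figures as before covariate adjustment. Show any assumed covariate gain separately, with its assumed strength.
4. Name the formula or simulation behind each figure, not only the software.

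The cost is one paragraph and a slightly less favourable stated power. Sample size, alpha, tests and models do not change.

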8.1 TRIAL APPROVAL, PATIENT INFORMATION, INFORMED CONSENT

This trial will be initiated only after all required legal documentation has been reviewed and approved by the respective IRB / EC and Competent Authority (CA) according to national and international regulations. The same applies for the implementation of changes introduced by amendments.

Prior to patient participation in the study, each prospective subject or their legally acceptable representative (in accordance with national legislation and ICH GCP) will be provided with all information relating to the study and a copy of the patient information and consent form.

Once the essential study information has been provided and the investigator is assured that each subject, or their legally acceptable representative, understands the implications of participating in the study, the subject, or their legally acceptable representative, will be asked to give consent to participate in the study by signing the informed consent form.

An independent impartial witness may be required in the event that the patient is able to give verbal consent, but unable to sign the consent form. In this case, the independent impartial witness will sign a form to indicate that the information was provided to the patient, the

patient appeared to understand the information and gave consent to participate in the study. The consent from the subject may be given verbally or by means of an unequivocal sign such as nodding or raising their hand in response to a question. The method used must be approved by the ethics committee and documented in the medical records.

If a short written informed consent document is initially used, once the patient recovers the investigator or delegate must discuss the study and sign the full patient consent and information sheet with the patient in order for patient to continue in the study. A note of the type of written informed consent obtained will be made in the subject's medical history/patient notes and recorded in the CRF.

An optional assessment of pharmacokinetics also is planned to be performed in at least 10 patients per dose group in Part 1 and in approximately 17 patients in Part 2. This pharmacokinetic sampling is voluntary and is not a prerequisite for study participation. Sampling will only occur after a separate pharmacokinetic informed consent has been given in accordance with the local ethics and regulatory requirements. Please refer to [Section 5.3.1](#) for more details on pharmacokinetic sampling process.

All signatures must be dated by each signatory and all completed consent forms will need to be retained by the Investigator and copies provided to the subject or the subject's legally acceptable representative.

Re-consenting may become necessary when new relevant information becomes available and should be conducted according to the sponsor's instructions. The consent and re-consenting process should be properly documented in the source documentation.

